4.1. Sample size

In REVIVED-BCIS2 all patients underwent viability imaging prior to randomisation; at least four viable segments which could be revascularised by PCI were required for inclusion. Of the 700 patients enrolled, viability was assessed with CMR in 491 and DSE in 187. Primary outcome data are available for 99.1% of patients. Serial echocardiographic data are available for a subset of these patients.

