4.2. Imaging processing

All viability studies will be analysed by one of two dedicated core laboratories: the King's College London Imaging Sciences CMR core laboratory (led by [name]) and the King's Health Partners Stress Echo core laboratory (led by [name]). Analyses will be performed by trained readers blinded to trial-group assignment and any other clinical data. Viability will be analysed on a segmental basis, using the AHA 17-segment model, excluding segment 17 (the left ventricular apex) as it is incompletely imaged on DSE and not included in CMR quantification. Transthoracic echocardiograms were analysed by the Guy's and St Thomas' echocardiography core laboratory with readers also blinded to the temporal sequence of echocardiograms.

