5.1. Wall motion scoring

For CMR and DSE, wall motion score will be classified on a five-point ordinal Likert scale as 1 – normal, 2 – hypokinetic, 3 – akinetic, 4 – dyskinetic, 5 – aneurysmal. For GSTT echocardiography core laboratory (non-DSE) measurements, the latter two points are combined into one category.

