8.4. Segmental LV function

Improvement in segmental function will be defined as an improvement in wall motion score ≥1 grade at follow-up. The frequency of functional recovery will be compared between segments based on scar transmurality/scar burden across time points using a repeated measures ANOVA to adjust for repeated measures within the same patient and over three time points of baseline, six months and one year. An unadjusted Cox regression model will be used to test for an interaction between scar transmurality/scar burden and the provision of revascularisation and the likelihood of functional recovery, adjusted for baseline segmental wall motion. Two models will be used for revascularisation; the first where all segments will be considered revascularised in patients who were assigned to PCI, the second where only segments where a territory was documented as having been successfully revascularised in the eCRF, with the attribution of segments based on the standard American Heart

^{*}indexed to body surface area

Association 17-segment model adjusted for dominance of the circumflex or right coronary artery ⁹. Equivalent analyses will also be performed with scar transmurality/scar burden substituted for end diastolic wall thickness/end systolic wall thickness, as well as for different thresholds of LGE for viability (≤50% and ≤ 75%) and where scar burden is treated as a continuous variable. Receiver-operator characteristic curve analysis will be used to examine diagnostic utility, with Youden's index used to calculate the LGE threshold for optimum sensitivity and specificity to predict functional recovery. DeLong's method will be used to compare ROC curves for the prediction of recovery between the FWHM and 5SD methods of defining regions of myocardial scar.

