The extent of inducible ischaemia will be determined on a per-patient basis. Ischaemic burden will be compared with myocardial jeopardy by converting both values to percentages of total LV volume (assuming a jeopardy score of 12 = 100% ischaemic burden. Kaplan-Meier plots for the primary outcome will be constructed based upon the presence/absence of significant inducible ischaemia (at least 1 segment of transmural ischaemia or 2 subendocardial segments in the same coronary territory) and based on the presence of ischaemia in >1 coronary vascular territory and separated by treatment assignment. A Cox regression model will be used to determine the effect of ischaemic burden on the primary outcome, key secondary outcomes and on global functional recovery, adjusted for treatment assignment and other key prognostic variables. A repeated measures ANOVA will compare the likelihood of functional recovery between segments with and without ischaemia, accounting for repeated measures in the same patient. A Cox regression model will be used to test for interaction between the presence of inducible ischaemia and segmental functional recovery, adjusted for segmental scar transmurality, wall thickness and revascularisation status. Further analyses will be performed where segmental ischaemia is defined as either a visible perfusion defect or a dysfunctional and viable segment¹⁵.

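### Viability SAP 8.4 puts segmental recovery, which is zero at baseline by definition, into a repeated measures ANOVA with baseline as a time point, so the time and scar-by-time tests are uninformative

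*Protocol*

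**What the plan says.** The analysis stands in Appendix 1 of the Viability Study SAP, which holds further analyses of the CMR data.

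- **Outcome (8.4, Segmental LV function):** "Improvement in segmental function will be defined as an improvement in wall motion score ≥1 grade at follow-up". This is a yes/no change status.
- **Underlying score (5.1):** "wall motion score will be classified on a five-point ordinal Likert scale".
- **Method (8.4):** "The frequency of functional recovery will be compared between segments based on scar transmurality/scar burden across time points using a repeated measures ANOVA".
- **Time points (8.4):** the ANOVA is described as "a repeated measures ANOVA to adjust for repeated measures within the same patient and over three time points of baseline"; the full list of times is "over three time points of baseline, six months and one year".
- **Related analysis (8.7, Inducible ischaemia):** "A repeated measures ANOVA will compare the likelihood of functional recovery between segments with and without ischaemia". This sentence mentions repeated measures within a patient but names no time points.

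Section 8.4 does not say that baseline is left out as an outcome time, that the ANOVA is run on the wall motion score, or that a model for binary data is used. No recovery rate, power or sample size is given for the segmental analysis.

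**The concern.** Recovery is measured relative to baseline, so at baseline it is zero, or undefined, for every segment. As a level of the outcome it carries no information and has no variance. A repeated measures ANOVA that includes it tests, in its time effect, whether any segment improves at all. That is true even if the only changes are re-reading differences. In its scar-by-time interaction it tests whether the scar groups differ at follow-up by more than zero, which is the scar effect again under another name. A reader shown these two tests could conclude that recovery progresses over the year, or that the influence of scar changes with time, when neither is so.

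The method also misfits the outcome more generally. ANOVA assumes a continuous response with comparable variance across times and groups. Here the response is binary, with a variance that depends on the recovery rate and is exactly zero at one of the three times.

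**Working it through.** **Inputs from the documents.** Three outcome times; binary recovery; "viability was assessed with CMR in 491 and DSE in 187"; 16 segments per patient, since section 4.2 analyses viability "using the AHA 17-segment model, excluding segment 17 (the left ventricular apex"). The upper limit is therefore 491 × 16 = 7,856 segments. Section 4.1 says serial echocardiography exists only for some patients and gives no number, so the actual count is lower and unknown. There is no planned figure to reproduce.

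**Assumptions, not from the documents.** Recovery of 1% to 40%, correlation of 0.6 between 6 and 12 months, 50 to 2,000 segments in each of two scar groups, independent segments, no true change between 6 and 12 months, 5% level, 500 simulated data sets per setting.

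**Step 1: the time effect.** With recovery p at both visits the profile over time is (0, p, p), with mean 2p/3. The departures from that mean are −2p/3, p/3 and p/3, so they vanish only if p = 0. The variances are 0, p(1 − p) and p(1 − p); at p = 0.40 these are 0, 0.24 and 0.24.

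**Step 2: the scar-by-time interaction.** With the same scar difference d at both visits, the profile of the difference is (0, d, d), with departures −2d/3, d/3 and d/3. An interaction appears although the scar effect is constant over follow-up. Without baseline the profile is (d, d) and there is none.

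**Step 3: the averaged scar difference.** Over three times it is (0 + d6 + d12)/3; over follow-up it is (d6 + d12)/2. The ratio is 2/3 for any d6 and d12:
- 0.20 and 0.20: 0.133 against 0.20
- 0.20 and 0.30: 0.167 against 0.25
- 0.30 and 0.30: 0.20 against 0.30

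**Step 4: the scar main-effect test.** Each segment's three-time mean is 2/3 of its follow-up mean. Between-group and between-segment sums of squares are both multiplied by (3/2) × (2/3)² = 2/3, so F and p do not change. In one simulated data set with 500 segments per group (40% versus 20%), the difference was 0.134 with baseline and 0.201 without, and F was 63.9 both ways.

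**Step 5: simulated share of significant tests, with baseline / 6 and 12 months only.**

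| Segments per group | Recovery by group | Time | Scar by time | Scar main effect |
|---|---|---|---|---|
| 2,000 | 40% v 20% | 100% / 6.0% | 100% / 5.0% | 100% / 100% |
| 500 | 40% v 20% | 100% / 6.4% | 100% / 5.2% | 100% / 100% |
| 50 | 40% v 20% | 100% / 6.8% | 63.8% / 6.4% | 70% / 70% |
| 500 | 30% v 30% | 100% / 4.6% | 4.8% / 4.2% | 5.4% / 5.4% |
| 2,000 | 1% v 1% | 100% / 4.6% | 3.8% / 4.0% | 4.2% / 4.2% |
| 50 | 10% v 10% | 99.2% / 4.6% | 5.2% / 4.6% | 5.4% / 5.4% |
| 50 | 4% v 2% | 37.2% / 1.8% | 6.4% / 2.0% | 4.8% / 4.8% |
| 50 | 2% v 2% | 17.4% / 1.4% | 2.0% / 0.2% | 0.6% / 0.6% |

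Runs with no recovery at all, which occurred only in the last two rows, are counted as not significant.

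**The case against.** The strongest reply is that section 8.4 asks whether recovery differs by scar, not whether it changes over time, and that the ANOVA is there to handle repeated measurement. On that question the zero baseline does no inferential harm. This stands: the scar main-effect F and p are identical with and without baseline. When the scar groups do not differ, the interaction test stays near or below its nominal level, so no false scar finding is created. A reader might infer that the scar comparison is diluted or loses power. The documents and the arithmetic do not support that. Only an average over all three times is scaled down, and the plan does not say that such an average will be reported.

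Three other inferences also go too far.

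- **That the time effect is always significant.** With 50 segments per group and rare recovery it was significant in 17% to 37% of runs.
- **That patients will be dropped, or that many lack a segment in some scar category.** The plan states neither. Section 6.4 refers other missing-data rules to the main SAP, which leaves modelling and imputation open.
- **That section 8.7 has the same baseline problem.** It names no time points, and its repeated measures may simply be several segments in one patient. Only the mismatch between ANOVA and a yes/no outcome carries over.

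Finally, the authors may have meant an ANOVA on the wall motion score itself, which is measured at all three times. That would be coherent in time structure, but section 8.4 names the frequency of recovery as what is compared. If the score was intended, the wording still needs to change.

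**Conclusion.** The point holds as a mismatch between a stated method and its outcome. A binary change from baseline is analysed with baseline as one of three outcome levels. The time effect is then near certain to be significant at large segment counts: 100% of runs at 500 or more segments per scar group, against about 6% without baseline. The scar-by-time interaction tends to be significant when scar groups differ, even by the same amount at both visits: 64% to 100% against about 5% for 40% versus 20% recovery, but only 6.4% with 50 segments per group and 4% versus 2%. Any scar difference averaged over the three times is two thirds of its follow-up value.

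The percentages rest on assumed recovery rates, correlation, segment counts and independence of segments. The two-thirds factor and the unchanged scar main effect follow from algebra when both follow-up values are present for each segment. Severity is minor: this is one secondary comparison in an appendix. The scar-by-revascularisation model and the ROC analysis in section 8.4 are specified separately from it, and the trial's primary result is unaffected.

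**What to change.** In section 8.4, drop baseline as an outcome time. Analyse recovery at 6 and 12 months with a mixed-effects logistic model, or GEE, containing scar category, visit, their interaction and baseline wall motion grade, with clustering by patient (and by segment across visits). Keep patients who have only one follow-up echocardiogram. This matches the plan's own choice in section 7.2, where a mixed model is used for ejection fraction so that incomplete series can contribute.

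Alternatively, state that the outcome is the ordinal wall motion score and model it over all three times, with the scar-by-time term carrying the question of recovery.

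In section 8.7, replace the ANOVA with the same kind of binary model, with ischaemia in place of scar category, and name the time points.

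The cost is a change of SAP wording. The models are standard and no new data are needed.

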8.1. Power Calculation

The predicted occurrence of death or hospitalisation for heart failure at two years is 36% in the OMT group(8, 19, 31, 41, 42). The primary endpoint in REVIVED-BCIS2 will be measured over the entire trial duration, with a minimum follow-up duration of two years, thus increasing the number of events. A trial of 700 (350 in each group) with 300 patients experiencing an event would have over 85% power to detect a hazard ratio of 0.7 (a 30% relative reduction in the hazard) at 5% significance allowing for up to 5% losses by the end of follow-up and increasing recruitment over time. For illustrative purposes this represents a reduction in death or hospitalisation to 27% in the PCI group at two years. The hazard ratio of 0.7 used in the power calculation is pragmatic, while being clinically meaningful and is in line with the magnitude of benefit observed across other treatment modalities in this population.

For the major secondary endpoint, even half this sample size will provide 90% power to detect a minimum difference in EF of 4%, assuming a standard deviation of 11%. The trial is expected to have very good power to detect differences in Quality of Life (one of the major secondary outcomes).

The above predicted event rates take into account the possibility of patients randomised to OMT subsequently undergoing PCI (see below). If a higher event rate is found in the OMT group or patient recruitment rates exceed expectation early in the trial (thus providing a

longer duration of follow-up in a larger proportion of patients), the trial would have greater power to detect a hazard ratio of 0.7, or alternatively, provide over 85% power to detect smaller differences in treatment effect.

Although a smaller treatment effect may be clinically significant, this would have a major impact on sample size, which in turn may affect the feasibility of completing the trial within the proposed timescale and resources.

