9.2. Wall motion score index prediction of LV recovery and mortality

The wall motion score index (WMSI) is a unitless number that is proportional to the severity and extent of wall motion abnormalities on stress echocardiography calculated by dividing the sum of the individual segment scores by the total number of segments scored. A WMSI >2.19 has been shown to be predictive of mortality or poor functional result in patients undergoing surgical revascularisation however this has yet to be tested in patient undergoing percutaneous coronary revascularisation. ROC curves will be constructed to identify a cut-off WMSI predicting poor outcomes in those undergoing percutaneous revascularisation.

9.3. Relationship between the number of viable segments on DSE and improvement in LV function following revascularisation

Using the AHA 16 segment model for analysis of regional wall motion score will allow the relationship between the total number of viable segments and global improvement in LV function to be explored; additionally segmental recovery will also be assessed using paired student's T test.

9.4. Comparison of sustained improvement in wall motion vs biphasic response of segments in predicting LV recovery

A biphasic response to dobutamine ("low vs high dose") has been found to be a more sensitive predictor of myocardial viability as compared with sustained improvement, moreover the biphasic response was found to be a predictor of global improvement in LV function after surgical revascularisation¹⁸. A comparison of sustained improvement vs biphasic response utilising Cox regression analysis will be carried out to identify if a biphasic response is a more sensitive predictor of myocardial recovery following percutaneous coronary revascularisation.

10. References

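### Viability SAP appendices: the segment- and territory-level Cox, ROC/DeLong and paired t-test analyses do not say how segments clustered within a patient are handled

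*Protocol*

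**What the plan says.** The Viability SAP is itself an analysis plan, so this is not detail left to a later document. Its two appendices add segment- and territory-level analyses.

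- **8.4, segmental function.** Recovery is an improvement of at least one wall motion grade in a segment. Frequencies are compared by repeated measures ANOVA, which is said to allow for several measurements in one patient. Then: "An unadjusted Cox regression model will be used to test for an interaction between scar transmurality/scar burden and the provision of revascularisation". The same sentence goes on to adjust this model for the segment's baseline wall motion. In the first of two versions of the exposure, every segment of a patient assigned to PCI counts as revascularised. ROC curves and Youden's index follow, and "DeLong's method will be used to compare ROC curves for the prediction of recovery between the FWHM and 5SD methods".
- **8.5, regional function.** A Cox model looks for predictors of recovery in vascular territories, several of which come from one patient.
- **8.7, ischaemia.** An ANOVA again accounts for the patient. Then: "A Cox regression model will be used to test for interaction between the presence of inducible ischaemia and segmental functional recovery".
- **9.3, stress echo.** "segmental recovery will also be assessed using paired student's T test".

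None of the Cox, ROC/DeLong or t-test statements mentions frailty, robust variance, a mixed model or resampling by patient.

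**The concern.** Randomisation is by patient, and segments of one heart share the operator, the medical therapy, the image quality and the patient's general course. Their outcomes are therefore likely to be correlated. A Cox model, DeLong's test or a paired t-test run in standard form counts each segment as a separate piece of information. If the correlation is material, standard errors for some terms are too small, and chance differences may be reported as effects of revascularisation, as interactions with scar or ischaemia, or as a better scar-quantification method. The plan recognises the issue for its two ANOVAs but not for the models that carry the interaction tests. An analyst following the text cannot tell whether the omission is intended, nor whether the 8.4 Cox model is adjusted.

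**Working it through.** **The plan's own figure.** There is none. No sample size, standard error, ICC or error rate is given for these analyses.

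**Inputs from the documents**
- Segments per patient, maximum: 17 − 1 = 16 (Viability SAP 4.2, "excluding segment 17 (the left ventricular apex) as it is incompletely imaged on DSE").
- A floor at inclusion, by site reading: "at least four viable segments which could be revascularised by PCI were required for inclusion" (4.1).
- Patients: "viability was assessed with CMR in 491 and DSE in 187" (4.1). Serial echo exists for an unstated subset.
- Level: 5%, stated only for the main power calculation (Protocol 8.1). Two-sided is assumed.

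**Assumptions.** All ICCs, recovery rates, 400 patients with follow-up echo, and 3 territories per patient.

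**Step 1: design effect.** DE = 1 + (m − 1) × ICC_y × ICC_x. Here m is segments per patient, ICC_y the outcome ICC and ICC_x the covariate ICC. ICC_x = 1 for a patient-constant term and for a mean change over segments. The naive type I error is 2 × [1 − Φ(1.96/√DE)].

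- m = 16, ICC_y = 0.01: DE = 1 + 15 × 0.01 = 1.15, giving 6.8%.
- m = 16, ICC_y = 0.05: DE = 1.75, giving 13.8%.
- m = 16, ICC_y = 0.10: DE = 2.50, giving 21.5%.
- m = 4, ICC_y = 0.05 to 0.30: DE = 1.15 to 1.90, giving 6.8% to 15.5%.
- 3 territories, ICC_y = 0.05 to 0.30: DE = 1.10 to 1.60, giving 6.2% to 12.1%.
- m = 16, ICC_y = 0.10, covariate varying within patient with ICC_x = 0.3: DE = 1 + 15 × 0.10 × 0.3 = 1.45, giving 10.4%.

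**Step 2: simulated Cox model for 8.4, no true PCI effect or interaction.** There were 400 data sets of 400 patients per row, with recovery seen at 6 or 12 months and Breslow ties. Terms were scar, assigned PCI, scar × PCI and baseline wall motion. The table shows rejection at |z| > 1.96.

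| m | Outcome ICC | Scar ICC | Naive, PCI | Naive, scar × PCI | Patient-clustered, PCI / interaction |
|---|---|---|---|---|---|
| 16 | 0.010 | 0.3 | 2.2% | 2.0% | 6.2% / 5.0% |
| 16 | 0.060 | 0.3 | 9.8% | 4.3% | 5.2% / 5.0% |
| 16 | 0.148 | 0.3 | 22.5% | 7.2% | 5.5% / 5.0% |
| 16 | 0.140 | 0.05 | 19.3% | 3.0% | 6.2% / 5.0% |
| 16 | 0.149 | 0.3* | 17.0% | 10.0% | 5.2% / 5.0% |
| 16 | 0.136 | 0.05* | 20.0% | 4.5% | 4.0% / 3.7% |
| 16 | 0.156 | 0.6 | 21.7% | 14.2% | 5.5% / 5.2% |
| 8 | 0.149 | 0.3* | 11.0% | 5.2% | 4.5% / 5.0% |

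*Scar slope also varies between patients.

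In the 16-segment rows with outcome ICC 0.136 or more, the true standard error of the PCI term was 1.51 to 1.58 times the naive one. For the interaction the ratio ran from 0.91 to 1.28. The first row shows that heavy ties make the naive Cox test conservative when there is almost no clustering, so Step 1 overstates the Cox inflation. With 400 data sets the Monte Carlo standard error near 5% is √(0.05 × 0.95/400) ≈ 1.1 percentage points.

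**Step 3: paired DeLong test, 16 segments, two methods of equal accuracy, outcomes clustered by patient.** Rejection was 3.5% when measurement error was independent between segments. It was 13.3% and 18.8% when the patient-level ICC of that error was 0.3 and 0.6. The true standard error of a single AUC was 1.19, 1.27 and 1.33 times the naive one.

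The second exposure version in 8.4 (documented revascularisation by territory), clustered ROC methods and a replacement for the t-test were not simulated.

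**The case against.** The strongest reply is that the text never says segments are independent. It is silent on the variance method, and a competent analyst who clusters the ANOVA might cluster the Cox model too. The 9.3 t-test might likewise be run on one summary per patient. That stands as far as it goes: the accurate statement is that clustering is not specified. But the named methods in standard form assume independent units, and the contrast with the ANOVAs leaves the intention open.

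A reader might infer that standard errors are too small throughout and that false-positive rates lie far above 5% in all these analyses. The documents do not support that. They give neither an ICC nor the number of analysable dysfunctional segments; 16 is a ceiling. For the scar by revascularisation test, scar varies within the patient, so inflation depends on how strongly scar clusters by patient. In several settings the naive test was at or below 5%. The DeLong difference behaves similarly.

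A reader might also infer that confidence limits for the optimal enhancement threshold would be too narrow. No interval is planned for the Youden cut-off, so that does not arise. Nor is a change of model family required: clustered standard errors on the planned Cox model were enough in every simulated setting.

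**Conclusion.** The point holds as an omission of stated method in 8.4, 8.5, 8.7 and 9.3, with a size that can only be given conditionally. Under the assumed outcome ICCs of about 0.06 to 0.16 with 16 segments, naive type I error is about 10 to 22% for patient-constant terms. It is about 3 to 14% for the scar interaction, according to how strongly scar clusters by patient. For the DeLong difference it is about 3.5 to 19%, according to how much measurement error is shared within a patient. Inflation is thus clear for terms such as assigned PCI and uncertain for the interaction. Fewer analysable segments reduce it.

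The reach is limited. Both appendices contain secondary analyses. The viability study's main analyses in sections 7.1 to 7.3 work at patient level, on the number of viable segments and global ejection fraction. They and the main trial result are unaffected. The conflict in 8.4 between *unadjusted* and adjustment for baseline wall motion is a separate, editorial defect.

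**What to change.** In 8.4, 8.5 and 8.7, state that segmental and territory recovery will be analysed with patient-clustered robust or shared-frailty Cox models. Mixed-effects logistic regression with a patient intercept, or GEE with patients as clusters, would serve equally. In 8.4, obtain standard errors for AUCs and AUC comparisons from a bootstrap that resamples patients, or from a ROC method for clustered data. In 9.3, replace the segmental paired t-test with a patient-clustered analysis of change. In 8.4, say once whether the Cox model is adjusted for baseline segmental wall motion, and delete the conflicting word. It would help to report the observed ICC and the number of analysable segments per patient.

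The cost is a few sentences in the SAP and standard commands on the same data. No new data are needed, and the result is far less dependent on whatever the ICC proves to be.
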